5. TREATMENTS AND EVALUATION

5.1. Dosing and Administration of Study Drugs and Other Medications

5.1.1. Dose/Dose Regimen and Administration

5.1.1.1 *Megestrol acetate* is supplied as either 40 mg (US) or 160 mg (Europe) tablets. For 40 mg tablets, two tablets are administered orally, twice daily, for a total daily dose of 160 mg. For 160 mg tablets, one tablet is administered orally, once daily, for a total daily dose of 160 mg.

At Study Visits when both megestrol acetate and Sodium Cridanimod are to be administered, the dose of megestrol acetate should be administered prior to Sodium Cridanimod. Whenever possible, the a.m. or p.m. dose of megestrol acetate should be taken in the clinic during the Study Visit.

5.1.1.2 *Sodium Cridanimod* solution is administered twice weekly according to either Schedule 1 (Mondays and Thursdays) or Schedule 2 (Tuesdays and Fridays) until documented disease progression, according to Table 8. For scheduled Sodium Cridanimod administrations that do not coincide with Study Visits, the Sodium Cridanimod can be administered either at the study site or at a subject's home by a medical service provider.

Table 8: Schedule of Sodium Cridanimod Administration

	Weekly until Disease Progression						
	Monday	Tuesday	Wednesday	Thursday	Friday	Saturday	Sunday
Schedule 1	500 mg i.m.			500 mg i.m.			
Schedule 2		500 mg i.m.			500 mg i.m.		

5.1.2. Dose Modifications

There will be no allowed modifications to the dosage, including dose reduction, of either megestrol acetate or Sodium Cridanimod during the trial.

If injection of Sodium Cridanimod was not administered on the scheduled dosing date, this can be done during the next two days but not later than 1 day before the next scheduled dose. The subsequent injection of Sodium Cridanimod should be given according to the study drug administration schedule.

If a subject misses a dose of megestrol acetate, the next dose should be taken at the regularly scheduled time.

Sodium Cridanimod and megestrol acetate combination therapy should be discontinued if an AE of Grade 3 or higher (according to NCI-CTCAE Version 4 criteria) is observed and determined to be potentially related to either medication. When combination treatment is discontinued, both Sodium Cridanimod and megestrol acetate are to be discontinued. Monotherapy in Treatment Period 2 is not permitted. The treatment will not be re-started and the subject will be withdrawn from Treatment Period 2. The subject will then enter the Follow-up Period as described in Section 5.1.4.

5.1.3. Duration of Therapy

5.1.3.1 Treatment Period 1: Subjects will participate in Treatment Period 1 for up to 24 weeks, during which time they are receiving only megestrol acetate. If a subject terminates therapy early in Treatment Period 1 for reasons outlined in Section 3.6, they will not be eligible to enter Treatment Period 2. They will have an End of Study Visit, and then be treated in accordance with local standards of clinical practice.

5.1.3.2 Treatment Period 2: Subjects who qualify to participate in Treatment Period 2 will receive both megestrol acetate and Sodium Cridanimod until documented disease progression. If a subject terminates therapy early in Treatment Period 2 for reasons outlined in Section 3.6, they will enter the Follow-up Period and then be treated in accordance with local standards of clinical practice.

5.1.4. Duration of Follow-up

There is no follow-up period for subjects exiting the study during or at the end of Treatment Period 1; they will continue to be treated in accordance with local standards of clinical practice.

Subjects who have participated in Treatment Period 2 and exit the study for any reason will enter the Follow-up Period. These subjects will return to the site 4 weeks following the discontinuation of treatment for the Safety Follow-up Visit. Subjects will then be followed for a 12-month period to determine overall survival. No additional visits are required after the Safety Follow-up Visit. Study staff will confirm survival status via telephone, personal contact or through clinic records, once, at the end of the 12 month period. This outcome is to be recorded in the eCRF.

5.1.5. Subject Compliance

Treatment compliance will be monitored by the review of study drug accountability, inventory records by study personnel, and patient diaries. Subject compliance (for each study drug individually) lower than 80% or higher than 120% will be considered a major protocol violation. In the case of poor compliance, the reason for the discrepancy will be documented in the eCRF and the Investigator, together with the Sponsor, will decide on a clinical basis as to whether the subject may remain in the study.

5.2. Demographics and Baseline Characteristics

5.2.1. Demographics

Year and month of birth, weight, height, and ethnic origin will be recorded.

5.2.2. Medical History

All current medical conditions, including endometrial cancer and any significant past conditions, surgeries, tobacco and alcohol consumption, previous therapeutic or diagnostic procedures, and all concomitant medications will be recorded.

5.3. Assessment of PrR Status at Screening

The PrR status of the endometrial cancer is determined at screening, through the assessment of an archived tumor sample. The archived sample should preferably be provided within Formalin-fixed Paraffin Embedded (FFPE) Block, but slides are acceptable. For confirmation of PrR status, the patient's tumor sample is sent to the central laboratory. Levels of PrR are determined with the use of semi-quantitative IHC. The tumor is considered to be PrR negative if the number of PrR positive cells is less than 1% determined by IHC. Conversely, the tumor is considered to be PrR positive if the number of PrR positive cells is 1% or greater as determined by IHC.

It is preferable to send the most recently obtained tumor sample whenever possible. Patients who cannot have PrR status confirmed by the central lab will be excluded from study participation.

5.4. Visit Schedule and Required Study Procedures

5.4.1. Screening (Time Frame: ≤ 4 weeks from the start of Treatment Period 1, Week -18 to -15)

- Informed consent
- Eligibility criteria
- Demographics
- Medical history
- Concomitant medication review
- Physical exam
- Vital signs

- Height
- Weight
- Performance status
- CBC with differential, platelets
- Serum chemistry
- eGFR
- Urinalysis
- Serum pregnancy test (for women of childbearing potential)
- ECG
- AE evaluation
- Confirmation of PrR status in central laboratory of archived tumor sample (*Specimen should be sent to central lab during Screening Weeks -18 and -16 to ensure results are received prior to Study Visit -3*).
- CT/MRI Scan
- Tumor assessment and measurements (*Radiologic evaluation must be obtained within 10 days of Visit -3*).

5.4.2. Treatment

Treatment Period 1 – Patients determined to have PrR Positive Status Only

Visit -3 (Week -14, ± 3 days) *

- Eligibility criteria
- Concomitant medication review
- Vital signs
- ECG
- For optional PK Sub-Study Participants:
 - Collection of blood samples for optional PK sub-study, at 10 timepoints: 0 (before administration of megestrol acetate), and 1, 2, 3, 4, 6, 24, 48, 72 and 96 hours (all times +/- 2 minutes) after administration).
- AE evaluation
- Administration of megestrol acetate
- Dispense supply of megestrol acetate
- Issue patient diaries

*** If Visit -3 occurs > 7 days after the Screening visit, the following assessments should also be performed:**

- Physical exam
- Weight
- Performance status
- CBC with differential, platelets
- Serum chemistry
- eGFR

Visit -2 (Week -8, ± 3 days)

- Concomitant medication review
- Physical exam
- Vital signs
- Weight
- Performance status
- CBC with differential, platelets
- Serum chemistry
- eGFR
- ECG
- AE evaluation
- Assess subject dosing compliance
- Collect completed patient diary(ies) and issue new diary(ies)
- Administration of megestrol acetate
- Collect any empty bottle(s) of megestrol acetate and dispense new supply

Visit -1 (Week -2, ± 3 days)

- Concomitant medication review
- Physical exam
- Vital signs
- Weight
- Performance status
- CBC with differential, platelets
- Serum chemistry
- eGFR
- ECG
- AE evaluation
- CT/MRI Scan
- Tumor assessment and measurements
- Assess subject dosing compliance
- Administration of megestrol acetate
- Collect completed patient diary(ies) and issue new diary(ies)
- Collect any empty bottle(s) of megestrol acetate

Visit TP1-EXT (Week +12, ± 3 days)

This treatment extension and visit is only for those subjects assessed to have disease control at Visit -1.

- Concomitant medication review
- Physical exam
- Vital signs
- Weight
- Performance status

- CBC with differential, platelets
- Serum chemistry
- eGFR
- ECG
- AE evaluation
- CT/MRI Scan
- Tumor assessment and measurements
- Assess subject dosing compliance
- Administration of megestrol acetate
- Collect completed patient diary(ies) and issue new diary(ies)
- Collect any empty bottle(s) of megestrol acetate

Subjects determined to have disease control (SD, PR or CR) confirmed by tumor assessment after 24 weeks in Treatment Period 1, will be **ineligible** to enter Treatment Period 2. The subject will be withdrawn from the study treatment and return for the End of Study Visit within 2 weeks to be discontinued from the study.

END OF STUDY VISIT (2 weeks after TP1-EXT, +/- 7 days)

For subjects who discontinue during TP1 for any reason (refer to Section 3.6) and those assessed to have disease control at Visit TP1-EXT:

Subjects to be discontinued from TP1 should complete the EOS as soon as withdrawal is determined.

Subjects assessed to have disease control at TP1-EXT should attend the EOS within 2 weeks of TP1-EXT Visit.

Subjects should continue their megestrol acetate dosing until the EOS unless the Investigator determines this is contraindicated.

- Concomitant medication review
- Physical exam
- Vital signs
- Weight
- Performance status
- CBC with differential, platelets
- Serum chemistry
- eGFR
- Urinalysis
- Urine Pregnancy Test (for women of childbearing potential)
- ECG
- AE evaluation
- Collect any outstanding patient diaries
- Collect all remaining megestrol acetate supplies

Subjects determined to have PrR negative status and subjects with documented disease progression after completing Treatment Period 1, will be eligible to enter Treatment Period 2.

Treatment Period 2

Visit 1, Day 0 (+/- 3 days) (Combination Treatment Start)

- Eligibility criteria
- Concomitant medication review
- Physical exam
- Vital signs
- Weight
- Performance status
- CBC with differential, platelets
- Serum chemistry
- eGFR
- ECG (before administration of Sodium Cridanimod and megestrol acetate, and 15, 60, 120, and 360 (\pm 5) minutes after administration of Sodium Cridanimod)
- For optional PK Sub-Study Participants:
 - Collection of blood samples for optional PK sub-study, at 10 timepoints: 0 min (before administration of Sodium Cridanimod and megestrol acetate), and 15 min, 30 min, 45 min, 60 min, 90 min, 2 hr, 3 hr, 4 hr, and 6 hr (all times +/- 2 minutes) after administration. Note additional PK draws below**
- AE evaluation
- Assess subject dosing compliance
- Collect completed patient diaries and remaining megestrol acetate for subjects completing Treatment Period 1
- Issue patient diaries
- Dispense supply of megestrol acetate
- Administration of megestrol acetate
- First administration of Sodium Cridanimod – The subject's condition will be monitored closely for a one-hour period after this first administration.

**** Days 3, 7, and 10 for optional PK Sub-Study Participants:**

Blood samples will be taken on Days 3, 7 and 10 (before administration of Sodium Cridanimod and megestrol acetate).

Visits 2, 6, 8, and 12 (Weeks 4, 20, 28, and 44; all \pm 3 days)

- Concomitant medication review
- Vital signs
- CBC with differential, platelets
- Serum chemistry
- eGFR
- ECG

- AE evaluation
- Assess subject dosing compliance
- Collect completed patient diaries and issue new diaries
- Collect any empty bottle(s) of megestrol acetate and dispense new supply
- Continued dosing of Sodium Cridanimod and megestrol acetate

Visit 3 (Week 8, ± 3 days)

- Concomitant medication review
- Physical exam
- Vital signs
- Weight
- Performance status
- CBC with differential, platelets
- Serum chemistry
- eGFR
- ECG (before administration of Sodium Cridanimod and megestrol acetate, and 15, 60, 120, and 360 (± 5) minutes after administration of Sodium Cridanimod)
- For optional PK Sub-Study Participants:
 - Collection of Day 56 blood sample for optional PK sub-study (before administration of Sodium Cridanimod and megestrol acetate)
- AE evaluation
- Assess subject dosing compliance
- Collect completed patient diaries and issue new diaries
- Collect any empty bottle(s) of megestrol acetate and dispense new supply
- Continued dosing of Sodium Cridanimod and megestrol acetate

Visits 4 and 10 (Weeks 12 and 36; both ± 3 days)

- Concomitant medication review
- Vital signs
- CBC with differential, platelets
- Serum chemistry
- eGFR
- ECG
- Visit 4 only - for optional PK Sub-Study Participants:
 - Collection of Day 84 blood sample for optional PK sub-study (before administration of Sodium Cridanimod and megestrol acetate) at Visit 4 only.
Does not occur at Visit 10.
- CT/MRI Scan
- Tumor assessment and measurements
- AE evaluation
- Assess subject dosing compliance
- Collect completed patient diaries and issue new diaries
- Collect any empty bottle(s) of megestrol acetate and dispense new supply

- Continued dosing of Sodium Cridanimod and megestrol acetate

Visits 5, 9, and 11 (Weeks 16, 32, and 40; all \pm 3 days)

- Concomitant medication review
- Physical exam
- Vital signs
- Weight
- Performance status
- CBC with differential, platelets
- Serum chemistry
- eGFR
- ECG
- AE evaluation
- Assess subject dosing compliance
- Collect completed patient diaries and issue new diaries
- Collect any empty bottle(s) of megestrol acetate and dispense new supply
- Continued dosing of Sodium Cridanimod and megestrol acetate

Visit 7 (Week 24, \pm 3 days)

- Concomitant medication review
- Physical exam
- Vital signs
- Weight
- Performance status
- CBC with differential, platelets
- Serum chemistry
- eGFR
- Urinalysis
- Urine Pregnancy Test (for women of childbearing potential)
- ECG
- CT/MRI Scan
- Tumor assessment and measurements
- AE evaluation
- Assess subject dosing compliance
- Collect completed patient diaries and issue new diaries
- Collect any empty bottle(s) of megestrol acetate and dispense new supply
- Continued dosing of Sodium Cridanimod and megestrol acetate

Beginning with Visit 13 (Week 48), study visits will occur every 12 weeks instead of every 4 weeks.

Visit 13, 14, 15, and continuing every 12 weeks until disease progression or other reason for withdrawal* (Weeks 48, 60, 72 etc.; all \pm 7 days)

- Concomitant medication review

- Physical exam
- Vital signs
- Weight
- Performance status
- CBC with differential, platelets
- Serum chemistry
- eGFR
- Urinalysis
- ECG
- CT/MRI Scan
- Tumor assessment and measurements
- AE evaluation
- Assess subject dosing compliance
- Collect completed patient diaries and issue new diaries
- Collect any empty bottle(s) of megestrol acetate and dispense new supply
- Continued dosing of Sodium Cridanimod and megestrol acetate

* Subjects continue administration of both Sodium Cridanimod and megestrol acetate until documented disease progression. If subjects have no evidence of progressive disease at Visit 13, they continue treatment as before, with visits to the Study Site continuing every 12 weeks thereafter until disease progression. At the visit where disease progression is documented, a new patient diary is not issued and no megestrol acetate is dispensed.

Subjects who discontinue from the study during Treatment Period 2 for reasons other than disease progression will enter the Follow-up Period and return for the Safety Follow-up Visit.

5.4.3. Follow-up Period (*Subjects participating in Treatment Period 2 only*)

Safety Follow-up Visit (Four [4] weeks following the last treatment of Sodium Cridanimod, \pm 3 days)

- Concomitant medication review
- Physical exam
- Vital signs
- Weight
- Performance status
- CBC with differential, platelets
- Serum chemistry
- eGFR
- Urinalysis
- Urine Pregnancy Test (for women of childbearing potential)
- ECG
- AE evaluation
- CT/MRI Scan

- Tumor assessment and measurements should be obtained whenever possible for subjects discontinuing for reasons other than disease progression (*unless a scan has been done within 4 weeks of withdrawal*).
- Collect any outstanding patient diaries
- Collect all remaining megestrol acetate supplies

Overall Survival Assessment (for 12 months after discontinuation of Treatment Period 2)

- Confirm survival status of subject via telephone, personal contact or through clinic records once, at the end of the 12 month period. No Study Visits are required. This outcome is to be recorded in the eCRF.

5.5. Efficacy Assessments

5.5.1. Visual Tumor Examination

The subject will undergo a clinical disease assessment for all palpable or visible lesions at the Screening Visit, and at Visits -1, TP1-EXT, and every 12 weeks in Treatment Period 2 to correlate with radiologic assessments.

5.5.2. Tumor Imaging and Measurement (CT/MRI)

Radiologic imaging with assessment and measurement of disease (CT or MRI scan of chest, abdomen, and pelvis) will be performed at the Screening, during Treatment Period 1 following 12 weeks of treatment (at Visit -1), and if disease control is achieved, after an additional 12 weeks of treatment (at Visit TP1-EXT), during Treatment Period 2 every 12 weeks (\pm 7 day window) until disease progression is documented.

In subjects with an objective response during Treatment Period 2, an additional radiologic assessment will be performed at least 4 weeks later to confirm the presence of an objective response. Response criteria is further outlined in Section 5.5.

Radiographic imaging may also be performed at any point during the trial the Investigator determines this is indicated. If disease progression is observed at an unscheduled scan during TP1, the subject is eligible to enter TP2 if she has received $>$ 4 weeks of treatment, otherwise the subject must return for an End of Study Visit and be discontinued from the trial. If disease progression is observed at an unscheduled scan during TP2, the subject must be withdrawn from treatment, enter the Follow-up Period and return for the Safety Follow-up Visit. An Unscheduled scan eCRF is to be completed.

5.5.3. Gynecologic Oncology Group (GOG) Performance Status

A subject will be assigned a GOG Performance Status at the Screening Visit and at Visits -3, -2, -1, TP1-EXT, EOS, 1, 3, 5, 7, 9, 11, 13, all subsequent quarterly Study Visits, and at the Safety Follow-up Visit, according to the following table:

Table 9. Performance Status Criteria

Gynecologic Oncology Group (GOG) Status Scale	
GOG Score	Descriptions
0	Fully active, unrestricted activities of daily living.
1	Ambulatory, but restricted in strenuous activity.
2	Ambulatory, and capable of self care. Unable to work. Out of bed for greater than 50% of waking hours.
3	Limited self care, or confined to bed or chair 50% of waking hours. Needs special assistance.
4	Completely disabled, and no self care.
5	Dead.

5.6. Assessment of Response

Tumor measurements will be collected by CT or MRI scan, as noted in Section 5.5.2. CT or MRI scan of chest, abdomen, and pelvis are appropriate, but all scans for an individual subject must use the same procedure as was performed at baseline. Conventional CT and MRI should be performed with contiguous cuts of 10mm or less in slice thickness. Spiral CT should be performed by use of a 5 mm contiguous reconstruction algorithm. Ultrasound should not be used for measurement. Clinically detected lesions will only be considered measurable if they are superficial (e.g. skin nodules and palpable lymph nodes). For skin lesions, documentation by color photography, including a tool to estimate size of the lesion, is recommended. Photographs should be retained with all other study documents at the study site.

In subjects with an objective response (as defined below), an additional CT/MRI scan and tumor assessment will be performed at least four weeks later to confirm the presence of objective response.

If a subject discontinues Treatment Period 2 for any reason other than disease progression (i.e. intolerable AE), every reasonable effort should be taken to encourage subjects to continue receiving regular CT/MRI scans and tumor assessments until disease progression is documented, with the date of disease progression still recorded in the eCRF.

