5.6.1. Measurable Disease Definitions

Important inclusion criteria for this trial include the presence of measurable disease with at least one target lesion to use for all disease assessments.

Measurable lesions are defined as those that can be accurately measured in at least one dimension (longest diameter to be recorded) as ≥ 20 mm by chest x-ray or as ≥ 10 mm with CT or MRI scan, or calipers by clinical exam. All tumor measurements must be recorded in millimeters (or decimal fractions of centimeters). For a lymph node to be considered pathologically enlarged and measurable, it must be ≥ 15 mm in short axis when assessed by CT scan (CT scan slice thickness recommended to be no greater than 5 mm).

Tumor lesions situated in a previously irradiated area, or in an area subjected to other loco-regional therapy, are not considered measurable unless there has been demonstrated progression in the lesion before study entry.

Non-measurable lesions are all other lesions, including small lesions (longest diameter <10 mm or pathological lymph nodes with ≥ 10 to <15 mm short axis), are considered non-measurable disease. Bone lesions, leptomeningeal disease, ascites, pleural/pericardial effusions, lymphangitis cutis/pulmonitis, inflammatory breast disease, and abdominal masses (not followed by CT or MRI), are considered as non-measurable.

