5.6.2. Definitions of Response

Target Lesions: All measurable lesions up to a maximum of 2 lesions per organ and 5 lesions in total, representative of all involved organs, should be identified as **target lesions** and recorded and measured at baseline. Target lesions should be selected on the basis of their size (lesions with the longest diameter), be representative of all involved organs, and in addition should be those that lend themselves to reproducible repeated measurements.

A sum of the diameters (longest for non-nodal lesions, short axis for nodal lesions) for all target lesions will be calculated and reported as the baseline sum of diameters. If lymph nodes are to be included in the sum, then only the short axis is added into the sum.

Table 10. Target Lesion Evaluation

Response	Definition
Complete Response (CR)	Disappearance of all target lesions. Any pathological lymph nodes (whether target or non-target) must have reduction in short axis <10 mm
Partial Response (PR)	At least a 30% decrease in the sum of diameters of target lesions, taking as reference the baseline sum diameters
Progressive Disease (PD)	At least a 20% increase in the sum of diameters of target lesions, taking as reference the smallest sum on study (this includes the baseline sum if that is the smallest on study). In addition to the relative increase of 20%, the sum must also demonstrate an absolute increase of at least 5 mm. The appearance of one or more new lesions is also considered progression.
Stable Disease (SD)	Neither sufficient shrinkage to qualify for PR nor sufficient increase to qualify for PD, taking as reference the smallest sum diameters while on study.

Non-Target Lesions: All other lesions (or sites of disease) including any measurable lesions over and above the 5 target lesions should be identified as **non-target lesions** and should also be recorded at baseline. Measurements of these lesions are not required, but the presence or absence of each should be noted throughout the study.

Table 11. Non-Target Lesion Evaluation

Response	Definition
Complete Response (CR)	Disappearance of all extranodal non-target lesions. All lymph nodes must be non-pathological in size (<10 mm short axis).
Non CR/Non PD	Persistence of one or more non-target lesion(s)

Progressive Disease (PD)	Unequivocal progression of existing non-target lesions. The appearance of one or more new lesions is also considered progression
--------------------------	--

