Appendix III. Frequently asked questions

Question	Answer
What should be done if several unique lesions at baseline become confluent at a follow-up evaluation?	Measure the longest diameter of the confluent mass and record to add into the sum of the longest diameters
How large does a new lesion have to be to count as progression? Does any small subcentimetre lesion qualify, or should the lesion be at least measurable?	New lesions do not need to meet 'measurability criteria' to be considered valid. If it is clear on previous images (with the same technique) that a lesion was absent then its definitive appearance implies progression. If there is any doubt (because of the techniques or conditions) then it is suggested that treatment continue until next scheduled assessment when, generally, all should be clear. Either it gets bigger and the date of progression is the date of the first suspicion, or it disappears and one may then consider it an artefact with the support of the radiologists
How should one lesion be measured if on subsequent exams it is split into two?	Measure the longest diameter of each lesion and add this into the sum
Does the definition of progression depend on the status of all target lesions or only one?	As per the RECIST 1.1 guideline, progression requires a 20% increase in the sum of diameters of all target lesions AND a minimum absolute increase of 5 mm in the sum
Are RECIST criteria accepted by regulatory agencies?	Many cooperative groups and members of pharma were involved in preparing RECIST 1.0 and have adopted them. The FDA was consulted in their development and supports their use, though they don't require it. The European and Canadian regulatory authorities also participated and the RECIST criteria are now integrated in the European note for guidance for the development of anticancer agents. Many pharmaceutical companies are also using them. RECIST 1.1 was similarly widely distributed before publication
What is the criterion for a measurable lesion if the CT slice thickness is >5 mm?	RECIST 1.1 recommends that CT scans have a maximum slice thickness of 5 mm and the minimum size for a measurable lesion is twice that: 10 mm (even if slice thickness is <5 mm). If scanners with slice thickness >5 mm are used, the minimum lesion size must have a longest diameter twice the actual slice thickness

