A listing of target lesions will present lesion site, description, measurement (in mm), type (nodal vs extranodal), whether the lesion is visible or palpable, was the lesion area previously irradiated, number of lesions assessed, method of assessment, CT/MRI slice thickness and whether contrast median was used. A second listing will summarize target lesion sums of diameters, percentage change from baseline, the investigator-determined overall time point target lesion assessment, sites of new lesions and method of evaluation of new lesions. This listing will also include percentage change from nadir, and which visits were used for baseline and nadir measurements for treatment period 2. Additionally, a listing of non-target lesions sites, description, status, investigator-determined overall time point non-target lesion assessment and number of non-target lesions assessed will be provided (including which visits were used for baseline assessments for subjects participating in Treatment Period 2).

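### Protocol 5.6.1 accepts 10 mm non-nodal lesions as measurable at any slice thickness up to the permitted 10 mm, whereas the appended RECIST 1.1 requires twice the slice thickness above 5 mm

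*Protocol*

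**What the plan says.** **Imaging.** Protocol 5.6 sets the limit for conventional CT and MRI: "Conventional CT and MRI should be performed with contiguous cuts of 10mm or less in slice thickness". The next sentence treats spiral CT separately: "Spiral CT should be performed by use of a 5 mm contiguous reconstruction algorithm". SAP Section 14 repeats both.

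**Measurability.** Protocol 5.6.1 sets the size for non-nodal lesions "as ≥ 10 mm with CT or MRI scan, or calipers by clinical exam", with no slice-thickness condition. Its only 5 mm wording is in the sentence on lymph nodes, and it is advisory: "CT scan slice thickness recommended to be no greater than 5 mm".

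**Target lesions.** Under Protocol 5.6.2 the target lesions are "All measurable lesions up to a maximum of 2 lesions per organ and 5 lesions in total".

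**Eligibility.** Inclusion criteria 4 and 5 (Protocol 3.4) require measurable disease and at least one target lesion, both by RECIST 1.1. The synopsis says that all scans are read by RECIST 1.1.

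**The appended guideline.** RECIST 1.1 Section 3.1.1 attaches the 10 mm CT minimum to slices of at most 5 mm. Section 3.2.2 and Appendix II give the rule for thicker CT slices, and Appendix III words it most firmly: "If scanners with slice thickness >5 mm are used, the minimum lesion size must have a longest diameter twice the actual slice thickness". Appendix III gives the same twice-thickness rule for MRI. Neither the protocol body nor the SAP restates it.

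**Data.** According to SAP Section 14, the target-lesion listing includes "method of assessment, CT/MRI slice thickness and whether contrast median was used".

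**The concern.** One eligibility criterion has two definitions. A site that follows 5.6.1 complies with the protocol body. A site that follows the appendix complies with the standard named in criteria 4 and 5. On slices above 5 mm they can reach different answers for the same lesion.

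This affects eligibility, because a subject whose only target lesion lies in the gap meets criterion 4 under one text and fails it under the other. Protocol 3.4 allows no waivers, and Protocol 7.7 and SAP 10.4 make any breach of an inclusion criterion a major deviation. The deviation status therefore depends on which text is read.

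It also affects response. The target-lesion sum determines PR and SD and contributes to PD, and PD governs entry to Treatment Period 2. Appendix II of the guideline asks that a measurable lesion be at least twice the slice thickness and refers to partial volume averaging in that context.

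**Working it through.** **Inputs**
- Largest permitted slice, conventional CT and MRI: 10 mm (Protocol 5.6, SAP Section 14).
- Spiral CT: 5 mm (same places).
- Minimum non-nodal size under the protocol body: 10 mm at any slice thickness (Protocol 5.6.1).
- Minimum under the appended guideline: 10 mm at slices of 5 mm or less, otherwise twice the slice thickness (RECIST 1.1 Sections 3.1.1 and 3.2.2, Appendices II and III).

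**Formula.** With slice thickness t in mm, the guideline minimum is max(10, 2 × t). The gap is the range from 10 mm up to, but not including, that minimum.

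**Reproducing the documents' figure.** At t = 5, 2 × 5 = 10 mm. This is the figure Appendix III gives, so the formula represents the rule correctly.

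**Applying it over the permitted range**

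| Slice t | 2 × t | Guideline minimum | Protocol 5.6.1 minimum | Lesions treated differently |
|---|---|---|---|---|
| 5 mm | 10 mm | 10 mm | 10 mm | none |
| 6 mm | 12 mm | 12 mm | 10 mm | 10 to <12 mm |
| 8 mm | 16 mm | 16 mm | 10 mm | 10 to <16 mm |
| 10 mm | 20 mm | 20 mm | 10 mm | 10 to <20 mm |

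**Cross-check within the appendix.** Appendix I records that RECIST 1.0 used 10 mm for spiral and 20 mm for non-spiral CT, and that version 1.1 dropped the distinction. Protocol 5.6 keeps a conventional/spiral split for slice thickness, but 5.6.1 applies 10 mm to both. A 10 mm lesion on a conventional CT with 10 mm cuts is therefore non-measurable under either version.

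**Nodes.** Protocol 5.6.1 requires a 15 mm short axis. Appendix III words the twice-thickness rule for longest diameter, so applying it to nodes is an assumption. If it were applied, a gap would open only where 2 × t > 15, that is t > 7.5 mm, and would reach 15 to <20 mm at t = 10. Nodes are left out of the finding.

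**Effect on a single 10 mm target lesion**
- PR needs a 30% decrease: 0.30 × 10 = 3 mm.
- PD through the sum needs 20%, 0.20 × 10 = 2 mm, and also an absolute increase of at least 5 mm. The 5 mm floor governs: 5 / 10 = 50%.

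**The case against.** **The 10 mm limit is not itself contrary to RECIST.** This is correct. The guideline accepts most slice thicknesses in clinical use and says how to handle thicker ones. The defect is the missing condition in 5.6.1, not the cut limit.

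**Sites may apply the appendix anyway.** This also stands. A reader might infer that the protocol body overrides the guideline and that subjects have been misclassified. No passage gives the body text precedence, and criteria 4 and 5 point to RECIST 1.1. The documents establish a conflict between two texts, not an actual misclassification.

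**Few scans may be affected.** Spiral CT is set at 5 mm, Appendix I says that most scans use slices of 5 mm or less, and Appendix II describes most current scanners as multidetector. The documents show no affected scan. The gap may be empty in practice, but they do not rule it out.

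**Safeguards exist.** The 5 mm absolute-increase rule limits false PD through the target sum. In Treatment Period 2, PR must be confirmed at least four weeks later. PR and SD both count as disease control, so calling SD a PR would not change ODCR. Protocol 5.6.1 asks for accurate measurement, and 5.6.2 for targets that can be measured reproducibly. A reader might also take the 3 mm PR threshold against a 10 mm slice as evidence of large measurement error. It is not: diameters on body CT are measured in the axial plane, and the documents give no error estimate. These safeguards reduce the consequences but do not reconcile the definitions.

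**The study is closing.** SAP Sections 1, 14.4 and 14.5 drop ODCR and ORR, and with 25 women already enrolled a wording change cannot alter past eligibility decisions. Lesion measurements, best overall response, duration of SD and PFS are still listed, and response appears in the swimmer's plot. A reader can already compare diameter with slice thickness by hand; a flag only makes this systematic.

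**Conclusion.** The inconsistency is real and limited. On conventional CT or MRI with slices above 5 mm, Protocol 5.6.1 accepts non-nodal lesions that the cited standard calls non-measurable: 10 to <20 mm at 10 mm slices, 10 to <16 mm at 8 mm, none at 5 mm or less. This rests only on the two written rules and on reading criteria 4 and 5 as invoking the appended guideline in full.

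The number of affected lesions and subjects cannot be derived from the documents, nor can the direction of any effect on response. A reader might infer a biased primary endpoint. The documents do not support that: no affected lesion is shown, and the SAP no longer calculates ODCR. What remains at stake is the eligibility and deviation status of individual subjects and the reading of the listed individual responses.

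**What to change.** **Text.** Add to Protocol 5.6.1 and SAP Section 14: *if CT or MRI slice thickness exceeds 5 mm, a non-nodal lesion is measurable only if its longest diameter is at least twice the slice thickness.* A 5 mm cap on slices would also close the gap, but it goes further than the guideline, which only recommends 5 mm.

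**Listings.** In Listings 16.2.6.1 and 16.2.6.2, flag each non-nodal target lesion whose diameter is below that minimum at the scan where it was selected as a target. The scan must be specified because baseline resets at Treatment Period 2. Mark the affected subjects in Listing 16.2.6.4.

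**What not to do.** Do not move lesions to non-target or re-derive response without them. Non-target lesions need a qualitative assessment that was not planned for these lesions, and a subject whose only target lesion was removed would have no sum to evaluate.

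**Cost.** One sentence in each document and one derived flag; slice thickness is already in the target-lesion listing. A few lesions, and possibly a subject's eligibility under criterion 4, would be shown as not meeting RECIST 1.1. These listings use the Full Analysis Set, which is restricted to subjects treated in Treatment Period 2, so the flag does not reach subjects who left during Treatment Period 1.
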